### **5.7. Blinding**

The patient will remain blinded to the randomization assignment from the time of randomization assignment to the end of the treatment

### **5.8. Enrollment Procedures**

Prior to enrollment, patients expressing an interest in participation will proceed with the inclusion/exclusion eligibility interview and informed consent process. An enrolled patient will be one who completes the eligibility interview, signs the Informed Consent form and receives initial treatment with either Restrata or Standard of Care therapy.

### **5.9. Device Application / Follow-up Care Procedures**

Please refer to Appendix C for a list of supplies that will be provided by the sponsor for wound assessments / follow-up care procedures.

#### **1) WOUND BED PREPARATION:**

- Prepare the wound bed using standard methods to ensure it is free of exudate and devitalized tissue. An initial excision or debridement of the wound is necessary to ensure the wound edges contain viable tissue.
- Wait for any bleeding to stop and ensure there is no active bleeding before applying synthetic hybrid-scale fiber matrix.
- Cleanse the wound thoroughly with sterile saline prior to application of synthetic hybrid-scale fiber matrix

#### **2) PREPARATION OF SYNTHETIC HYBRID-SCALE FIBER MATRIX**

- Select the appropriate size sheet of synthetic hybrid-scale fiber matrix.
- **Heavily fenestrate with a scalpel or mesh prior to application.**  
Synthetic hybrid-scale fiber matrix must be fenestrated prior to use

in any wound prone to exudate in order to permit effective exudate management.

- Synthetic hybrid-scale fiber matrix is packaged in a nested pouch configuration. Peel open the outer foil pouch starting from the chevron sealed edge. The inner TyVek® pouch is sterile and may be placed on the sterile field.
- Rinse surgical gloves, if necessary, to remove any glove powder prior to touching the product.
- Synthetic hybrid-scale fiber matrix can be cut to the desired shape in a wet or dry state. In order to increase pliability of the product, hydrate in warm, sterile, hypertonic solution (i.e. saline, water, etc.) for a minimum of 1 minute.

### **3) APPLICATION OF SYNTHETIC HYBRID-SCALE FIBER MATRIX**

- Apply matrix with either side towards the wound bed, and position to completely contact the entire surface of the wound bed and extend slightly beyond wound margins. The matrix can be repositioned as necessary.
- Securely anchor the matrix as needed with suture, staples or Steristrips.
- Apply a non-adherent primary wound dressing over the matrix.
- To prevent dislodgment of product, apply appropriate secondary dressing or compression to maintain dressing adherence (e.g., multi-layer compression bandage system, or other appropriate dressing), manage the wound exudate, keep the matrix moist, and keep all layers securely in place. The optimum secondary dressing is determined by wound location, size, depth and provider preference.
- Discard any unused pieces of study product BEFORE the curtain between the patient's head and lower extremities is opened.
- Provide appropriate offloading device as appropriate based on the subject's wound location, health status etc.

#### **5.10. Standard of Care**

##### **1) WOUND BED PREPARATION:**

- Prepare the wound bed using standard methods to ensure it is free of exudate and devitalized tissue. An initial excision or debridement of the wound is necessary to ensure the wound edges contain viable tissue.
- Wait for any bleeding to stop and ensure there is no active bleeding before applying an appropriate primary dressing.
- Cleanse the wound thoroughly with sterile saline prior to application of an appropriate primary dressing.

## **2) APPLICATION OF PRIMARY / SECONDARY DRESSINGS**

- Apply primary dressing to the wound bed, and position to completely contact the entire surface of the wound bed and extend slightly beyond wound margins.
- Securely anchor the dressing as needed.
- Apply appropriate secondary dressing to maintain dressing adherence, manage the wound exudate, and keep all layers securely in place. The optimum secondary dressing is determined by wound location, size, depth and provider preference.
- Discard any unused pieces of standard wound therapy BEFORE the curtain between the patient's head and lower extremities is opened.
- Provide appropriate offloading device as appropriate based on the subject's wound location, health status etc.

### **5.11. Post-Application Procedures**

- Patients should be instructed on how to care for the wound site, utilize an appropriate offloading device (CAM boots or surgical shoes), and keep the wound site moist, and clean.
- Patients are required to return to the clinic every week for post-operative analysis of the wound site.

## **5.12. Follow-Up Procedures**

Weekly up to 12 weeks or until complete closure is first identified with a confirmation visit within 2 weeks thereafter; window for all visits is  $\pm$  3 days. At each of the interim timepoints subjects will return to the clinic for analysis / assessment of the following as indicated in the Schedule of Events in Appendix A:

- Measurement of wound area
- Documentation of wound appearance via photograph
- Documentation of wound closure (if present)
- Gross observation of wound for evidence of infection
- Assessment of Quality of Life
- Codes used to submit for reimbursement and amount (if any) reimbursed

## **5.13. Study Exits**

### **5.13.1. Study Participation Exit Points**

A patient's participation in the study will end after any of the following:

- Patients with complete re-epithelialization and closure confirmation
- Patients without complete re-epithelialization at 12 weeks
- Patient withdrawal
- Patient lost to follow-up
- Amputation of all or part of the study limb
- Closure of study
- Patient death

### **5.13.2. Patient Withdrawal**

A patient (or patient's LAR) may choose to withdraw from the study at any time without penalty or loss of benefits. The patient should notify the investigator (or designee) of his/her desire to withdraw, and the investigator (or designee) should ask for and document the reason for withdrawal. The investigator may also choose to withdraw a patient from the study at any time if he/she considers it to be in the patient's best interest. The reason for withdrawal should be recorded. Any data collected on the patient up to the point of withdrawal may be used in the study.

If complete wound closure has not been confirmed at the time of withdrawal from the study, then the investigator should attempt to

determine the status of the wound at the time of the patient's withdrawal to the best of the patient's ability (i.e., healed, not healed, seeking additional treatment, not seeking additional treatment) and to complete as many of the patient-reported outcomes questionnaires as the patient is able and willing to complete.

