## **3. STUDY DESIGN**

**Condition:** Diabetic Foot Ulcer (DFU)

**Aim:** Comparatively assess wound closure in diabetic foot ulcers treated with synthetic hybrid-scale fiber matrix or standard of care in a randomized, controlled clinical trial.

**Number of Patients:** 48 subjects (24 subjects in the experimental arm and 24 subjects in the control arm)

**Number of Sites:** 2

**Study Type:** Interventional

**Study Design:** Allocation: Randomized (1:1 ratio)  
Endpoint Classification: Efficacy  
Intervention Model: Direct assignment

Masking: Single Blind (Subject)

Primary Purpose: Treatment

**Control Group:** Treatment with Standard of Care (weekly)

**Test Group:** Treatment with Synthetic Hybrid-Scale Fiber Matrix (weekly or as needed based on the clinician discretion and ongoing wound assessment)

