#### **5.13.3. Patient Lost To Follow-Up**

The investigator should encourage patients to return for all required follow-up visits. A patient will be considered lost to follow-up after three documented phone call attempts or emails plus a certified letter that is sent to the patient's last known address in which no response is received. A patient should not be automatically exited from the study after a missed visit(s). Rather, the patient will remain in the study until he/she completes the final study visit required by the protocol, withdraws from the study, or is considered to be lost to follow-up.

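### Section 5.13.2 lets an unmasked investigator withdraw a patient from the study on a best-interest judgment, and then does not ask for week-12 closure even if the patient could still attend

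*Combined protocol and SAP*

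**What the plan says.** Section 5.13.1 states that a patient's "participation in the study will end after any of the following" and lists seven exit points. Patient withdrawal is one of them. Stopping assigned treatment is not.

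Section 5.13.2 covers withdrawal by the patient. It adds a second route, decided by the investigator, who on his or her own judgment "may also choose to withdraw a patient from the study at any time if he/she considers it to be in the patient's best interest". A reason has to be recorded, and data collected up to withdrawal may be used. If closure has not been confirmed, the investigator is asked to try to "determine the status of the wound at the time of the patient's withdrawal to the best of the patient's ability". The status options are healed or not healed, and seeking or not seeking additional treatment.

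Two passages favour retention. Section 5.12 ties visits to time and closure, not to receiving product: "Weekly up to 12 weeks or until complete closure is first identified with a confirmation visit within 2 weeks thereafter". Section 5.13.3 says a missed visit alone is no reason for exit: "the patient will remain in the study until he/she completes the final study visit required by the protocol, withdraws from the study"; loss to follow-up also ends it.

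Section 3 masks the subject only. It also allows as-needed application in the test group and lists control treatment as weekly. Section 7.2 makes mITT the primary efficacy population, analysed as randomised. Section 7.8 imputes missing closure status by logistic multiple imputation with 50 datasets. The named predictors are age and gender; the others are left to the formal SAP.

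**The concern.** The primary endpoint is closure within 12 weeks, confirmed 2 weeks later. Wound status at week 5, say, cannot supply it. The best-interest sentence removes a patient from the study, not merely from treatment, and no sentence asks for the week-12 assessment when the patient is willing and able to attend. The decision is made by someone who knows the arm and sees the wound.

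The mITT analysis still needs an outcome for that patient. An outcome that could have been observed may therefore be replaced by a model-based one, after a decision that can depend on both arm and healing progress. With 24 patients per arm, one patient is 1/24 = 4.2 percentage points of an arm's closure rate. A few withdrawals that are unbalanced between arms could move a borderline result.

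**Working it through.** **Starting point.** The plan gives no rate of investigator withdrawal, so there is no figure of its own to reproduce on this point. The size below is an illustration.

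**Inputs from the documents.** 24 per arm (sections 1 and 3); closure 80% v 40%, margin +10%, one-sided alpha 0.05, Farrington-Manning test (7.3); 50 imputations (7.8).

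**Assumptions.** One or two withdrawn patients in an arm, all truly unhealed at week 12. They are treated as missing and imputed either at the closure rate of the arm's remaining patients or at half that rate, the latter standing for an imputation model that reflects slow progress. Single stage, no sample-size increase.

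**Shift in an arm's closure rate when two patients are imputed at the planned rate:**
- Restrata, truly unhealed: 2 × 0.80 / 24 = +6.7 points. Truly healed: −2 × 0.20 / 24 = −1.7 points.
- Control, truly unhealed: 2 × 0.40 / 24 = +3.3 points. Truly healed: −2 × 0.60 / 24 = −5.0 points.

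**Test.** z = (p1 − p2 − 0.10) / √{[q1(1 − q1) + q2(1 − q2)] / 24}, where q1 and q2 are the restricted maximum-likelihood estimates with q1 − q2 = 0.10. After imputation the mean difference replaces p1 − p2. The variance becomes W + (1 + 1/50)B (Rubin's rules; W within and B between imputations, expected values, normal reference).

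**One table by hand: 18 v 10 closures.** The difference is 8/24 = 0.333, q1 = 0.638, q2 = 0.538, and the variance is 0.01999. Then z = 0.2333 / 0.1414 = 1.65 and p = 0.049, a success. Now withdraw two unhealed controls and impute them at 40%. The mean difference is (18 − 10.8)/24 = 0.300, B = 2 × 0.4 × 0.6 / 24² = 0.00083, and W ≈ 0.0197. Then z = 0.200 / √0.0206 ≈ 1.39 and p = 0.081, a failure. With two withdrawn in each arm, p = 0.031. By contrast, 19 v 10 (p = 0.025) stays a success either way: p = 0.007 with two Restrata patients withdrawn, 0.044 with two controls.

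**All possible tables at 80% v 40%.** Each of the 25 × 25 outcomes is weighted by its binomial probability. Complete follow-up succeeds in 72.9% of trials.

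| Unhealed patients withdrawn (Restrata, control) | Result changes, remaining rate | Result changes, half rate | Result changes, not healed counted as non-closure |
|---|---|---|---|
| 2, 0 | 13.45% (failure to success) | 6.3% | 0% |
| 0, 2 | 8.4% (success to failure) | 8.1% | 0% |
| 2, 2 | 4.4% (failure to success) | 2.7% | 0% |

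A simulation with 50 actual draws per trial (8,000 trials per case) gave 13.5%, 9.4% and 4.9% at the remaining rate, and 5.6%, 7.2% and 2.6% at half rate.

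**True difference at the margin (50% v 40%).** False success is 5.05% with complete follow-up. At the remaining rate it is 11.55% (2, 0), 3.7% (0, 2) and 6.7% (2, 2). At half rate it is 6.8%, 3.8% and 6.7%.

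The 72.9% at 24 per arm is below the power of 0.8 that section 7.3 states for 20 per group. That is a separate matter, and nothing here depends on it.

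**The case against.** **The default is retention.** A reader might infer that section 5.13 makes stopping treatment the same as leaving the study. The documents do not support that. Stopping is not a listed exit, sections 5.12 and 5.13.3 keep the patient in, and as-needed application lets a test-arm patient go without product and stay. This stands, and it narrows the point to the investigator's best-interest withdrawal. It does not remove the point, because section 5.13.3 itself releases a patient who withdraws.

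**Imputation is inferred.** Section 7.8 imputes only patients whose closure status is missing, and section 5.13.2 asks for a healed or not-healed status at exit. No passage says how a recorded not-healed status is used. If it counts as non-closure, every change in the table is 0%. This also stands. Closure by week 12 is unobserved under either reading.

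**The sizes are driven by assumptions.** The 13% needs both withdrawals in Restrata, both truly unhealed, and an imputation that ignores slow progress. Weekly wound data are collected, and the formal SAP may put them in the model. At a quarter of the remaining rate the figure falls to 3.2%. Part of the effect is the discreteness of the test: one control withdrawal changes 8.1% of results and two change 8.4%. Patients who would have healed shift the rates the other way and are not in the table. All of this is right.

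**Best-interest withdrawal protects patients.** It does, and it should stay. Study visits can themselves be against a patient's interest, for example in severe intercurrent illness. Limiting withdrawal to withdrawal of consent would go too far.

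**Conclusion.** The point holds in its narrow form. An investigator who is not masked may end a patient's participation on a best-interest judgment, and the plan then seeks only wound status at exit. Closure by week 12 is lost for a patient who could have attended visits that are already scheduled.

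Frequency is unknown. A reader might infer that the rule favours Restrata; the documents give no direction, and the calculations go either way according to which arm loses patients and whether they would have healed. Under the stated assumptions, between about 3% and 13% of trial results change with two withdrawals in one or both arms, and 0% if not healed at exit is counted as non-closure. Most trials keep their result in every case, and balanced withdrawals matter least. The recorded reason, exit status and weekly data limit the loss but do not replace the endpoint.

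This is a cheap improvement, not a flaw that invalidates the design.

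**What to change.** In sections 5.13.1 and 5.13.2, state that when the investigator stops assigned treatment or starts another wound product in the patient's interest, the patient stays in the scheduled weekly visits. At minimum, the patient has a week-12 evaluator assessment, with the 2-week confirmation if the wound is closed. Both apply provided the patient agrees. Keep the investigator's right to end participation when the visits themselves are against the patient's interest, and keep withdrawal of consent as it is.

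Add the date of stopping and any other wound product used to the reason and additional-treatment status already collected. Analyse these patients as randomised. For those who still leave early, say in section 7.8 or the formal SAP whether not healed at exit is missing or non-closure.

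The cost is protocol, consent and CRF wording, and a few follow-up visits for patients off assigned treatment. The visits already exist in section 5.12 and Appendix A.

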#### **5.13.3. Patient Lost To Follow-Up**

The investigator should encourage patients to return for all required follow-up visits. A patient will be considered lost to follow-up after three documented phone call attempts or emails plus a certified letter that is sent to the patient's last known address in which no response is received. A patient should not be automatically exited from the study after a missed visit(s). Rather, the patient will remain in the study until he/she completes the final study visit required by the protocol, withdraws from the study, or is considered to be lost to follow-up.

#### **5.13.4. Patient Death**

If known, the cause of death should be documented.

#### **5.13.5. Sponsor Discontinues Study**

Premature termination of this clinical study may occur because of a regulatory authority decision, change in opinion of the IRB/EC, product safety concerns or at the discretion of Acera Surgical, Inc. Acera Surgical, Inc. reserves the right to discontinue the study prior to inclusion of the intended number of patients but intends only to exercise this right for valid scientific or administrative reasons. After such a decision, the investigator must contact all participating patients within 30 days.

### **6. ADVERSE EVENT**

#### **6.1. Principal Investigator Responsibilities**

The investigator (or designee) should record and maintain all adverse events that occur over the course of the patient's participation in the study (randomization through study exit) during or outside of study visits. Adverse events that are reported to the sponsor will be assessed by an investigator. Adverse event assessments should include severity, seriousness, and relatedness to the product, study procedures and pre-existing conditions. See Section 6.4 for adverse events that are required to be reported to the Sponsor.

## 6.2. Adverse Event Definitions

### Adverse Event:

Any untoward medical occurrence (sign, symptom, illness, abnormal laboratory value, or other medical event) that occurs while the patient is enrolled in the study whether or not it is related to the study product or study procedures. A medical condition (pre-existing condition) that exists at study enrollment/randomization is not considered an AE unless the condition worsens after enrollment.

### Serious Adverse Event:

A serious adverse event is any undesirable adverse event or untoward medical occurrence (sign, symptom, illness, abnormal laboratory value, or other medical event) experienced by a patient during the study that:

- Results in death;
- Is life-threatening;
- Requires inpatient hospitalization or prolongation of an existing hospitalization;
- Results in persistent or significant disability/incapacity; or
- Requires intervention to prevent a permanent impairment of a bodily function or damage to a body structure.

Medical and scientific judgment should be exercised in determining whether an event is a serious adverse event. An important medical event may not be immediately life-threatening and/or result in death or hospitalization. However, if it is determined that the event may jeopardize the patient and may require intervention to prevent one of the other outcomes listed in the definition above, the adverse event should be reported as serious. Examples of such events are intensive treatment in an emergency room for a bronchospasm or convulsions that do not result in hospitalization.

This definition of an SAE is not intended to include hospitalization specifically to treat a condition that existed prior to the patient's enrollment in the study (e.g., pre-existing cardiovascular disease that is treated during the study) or prearranged elective surgery performed during this study period.

### Adverse Device Effect:

Any adverse event that is caused by or associated with a study product.

#### **Unanticipated Adverse Device Effect:**

Any serious adverse effect on health or safety or any life-threatening problem or death caused by or associated with a study product, if that effect, problem or death was not previously identified in nature, severity or degree of incidence in the Protocol or Instructions for Use.

#### **6.3. Adverse Event Assessment**

Adverse events that are required to be reported to the sponsor must be assessed by an investigator for severity, seriousness and relatedness to the product, study procedures and pre-existing conditions.

The following scale should be used for severity assessment:

ADVERSE EVENT SEVERITY	
Mild	AE is noticeable to the patient but does not interfere with routine activity and does not require medical treatment
Moderate	AE interferes with routine activity and/or requires medical treatment
Severe	AE results in loss of life, loss of limb, is life threatening, or results in permanent impairment of body structure or function

The following scale should be used for an assessment of relatedness to the study product, study procedure(s), and pre-existing conditions:

- Not Related
- Possibly Related
- Probably Related
- Definitely Related

#### **6.4. Adverse Event Reporting**

The following adverse events are required to be promptly reported to the sponsor on the adverse event CRF:

- Any serious adverse event whether or not it is related to a study product/procedure

- Any adverse event that in the opinion of the investigator is definitely related, probably related, or possibly related to a study product and/or study procedure
- The following adverse events whether or not they are related to a study product/procedure:
  - Infection of wound and/or area surrounding wound
  - Complete or partial amputation of lower extremity
  - Allergic reaction

Serious adverse product effects should be reported to the sponsor as soon as possible. Pre-existing conditions or adverse events that occur prior to randomization are not required to be reported.

The investigator (or designee) is also required to report AEs to the IRB/EC if the AEs are required to be reported per the IRB/EC reporting requirements.

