### **7.7. Adverse Events**

#### **7.7.1. All Adverse Events**

Summaries of incidence rates of individual AEs overall will be prepared. Only treatment emergent AEs will be analyzed (a treatment emergent adverse event is one that started or worsened in severity at or after start of randomized treatment). Because a patient may experience more than one AE, summaries will provide both the number of patients experiencing at least one event and the number of events within a reporting period. Percentages provided will be the percent of patients experiencing one or more adverse events. In addition, incidence of AEs will be presented by severity (mild,

moderate, severe) and by relationship to investigational product or procedure. Patients experiencing an event more than once will be counted under the maximum severity/relationship experienced.

A listing of all adverse events will include the patient number, AE number, days since index procedure, the AE name, the severity of AE, whether or not the AE is classified as serious (SAE), the relationship of the AE to the study product or procedure, the action taken, and the outcome.

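### The all-adverse-event tables in 7.7.1 and one event of interest in 7.7.3 promise more than Section 6.4 requires on the CRF, so overall rates may be too low and the arms may not be comparable.

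*Combined protocol and SAP*

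**What the plan says.** **Recording at site.** Section 6.1 is broad: "The investigator (or designee) should record and maintain all adverse events that occur over the course of the patient's participation in the study", from randomization to study exit. It then sends the reader to Section 6.4 for what must reach the sponsor.

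**Entry on the CRF.** Section 6.4 opens with "The following adverse events are required to be promptly reported to the sponsor on the adverse event CRF" and gives three routes:
- Serious events, without regard to cause: "Any serious adverse event whether or not it is related to a study product/procedure".
- Related events: those that the investigator considers at least possibly linked to the product or a procedure of the study.
- Named events, entered whatever the judged cause: wound infection, lower-extremity amputation and allergic reaction.

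**Grading.** Section 6.3 ties grading to the same set: "Adverse events that are required to be reported to the sponsor must be assessed by an investigator for severity, seriousness and relatedness".

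**Analysis.** Section 7.7.1 is titled as covering all adverse events and states: "Summaries of incidence rates of individual AEs overall will be prepared". It adds tables by severity and by relationship, and a listing of all events. Nothing in it limits these outputs to reportable events. Section 7.5 has all results shown by treatment group. Section 7.7.3 tabulates four events of interest by treatment group; the fourth covers excessive redness, pain, swelling or blistering of the wound.

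**Status and masking.** Adverse event incidence is a tertiary outcome (Section 3), and Section 7.6.3 treats tertiary endpoints as exploratory summaries. Section 3 masks the subject only.

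**The concern.** The analysis section describes a complete count of treatment-emergent events. The collection section requires only a subset in the data from which that count would be made. The events left out are not a random sample: they are the non-serious events, outside three named types, that the investigator judges unrelated.

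Two things are at stake. First, rates presented as all-event incidence may understate what happened to patients in either arm. Second, the investigator who judges relatedness is not masked, and only one arm receives the study product. If knowledge of the arm affects that judgement, it affects which non-serious events are counted at all, as well as how they are classified. A difference between arms in the tables could then partly reflect reporting.

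**Working it through.** The plan states no figure on this point, so there is none to reproduce. The check compares the sections and then gives an illustration under assumed inputs.

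**1. Which events must be entered on the CRF and graded?**

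| Type of event | Site record (6.1) | CRF entry required (6.4) | Grading required (6.3) | Planned output |
|---|---|---|---|---|
| Serious, related or not | Yes | Yes | Yes | 7.7.1, 7.7.2 |
| Wound infection, amputation, allergic reaction, related or not | Yes | Yes | Yes | 7.7.1, 7.7.3 |
| Other non-serious, at least possibly related to product or procedure | Yes | Yes | Yes | 7.7.1 |
| Other non-serious, judged not related | Yes | No | No | 7.7.1 |
| Non-serious redness, pain, swelling or blistering, judged not related | Yes | No | No | 7.7.1, 7.7.3 |

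The last two rows are the gap. Both kinds of event are promised in an output, and neither has a required route to the database or a required grade.

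**2. Where does the relatedness call decide entry?** Only for non-serious events outside the three named types. Serious and named events enter whatever the call.

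**3. Is the call symmetric between arms?** Partly. Section 6.4 counts relation to a study procedure as well as to the product. Under Section 5.10, control patients also have debridement and dressings, so their events can qualify as procedure-related. Relation to the product itself is possible only in the matrix arm.

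**4. Illustration.** None of the following rates comes from the documents. Let r be the true risk, equal in both arms, of a non-serious, unnamed event, and c the chance that it is called at least possibly related. The tabulated risk is r × c.

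| Assumed r | Assumed c, matrix | Assumed c, control | Tabulated, matrix | Tabulated, control |
|---|---|---|---|---|
| 20% | 50% | 10% | 0.20 × 0.50 = 10% | 0.20 × 0.10 = 2% |
| 40% | 50% | 10% | 0.40 × 0.50 = 20% | 0.40 × 0.10 = 4% |
| 60% | 50% | 10% | 0.60 × 0.50 = 30% | 0.60 × 0.10 = 6% |
| 40% | 30% | 10% | 0.40 × 0.30 = 12% | 0.40 × 0.10 = 4% |
| 40% | 30% | 30% | 0.40 × 0.30 = 12% | 0.40 × 0.30 = 12% |

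In patients, with 24 per arm and r = 40%, 24 × 0.40 = 9.6 per arm have such an event. With 50% versus 10% capture, about 24 × 0.20 = 4.8 and 24 × 0.04 = 1.0 are tabulated. With equal 30% capture there is no false difference, but 1 − 0.30 = 70% of affected patients are missing from both arms.

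**The case against.** **Section 6.4 may be only a rule on timing.** Its lead-in concerns prompt reporting. Section 6.1 has all events recorded, Appendix A marks adverse events at week 0, the weekly visits and the follow-up visit, and 7.7.1 specifies a listing with severity and relationship fields. On this reading every event reaches the CRF, and 6.4 says only which are urgent. The CRF is not in the documents, so the reading cannot be excluded. But no section gives a slower CRF route for the remaining events, Appendix A does not say what the CRF covers, 6.1 itself defers to 6.4, and 6.3 does not require the remaining events to be graded. What stands is that omission is permitted, not shown.

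**The importance is limited.** Adverse event incidence is tertiary and descriptive, and three of the four events of interest in 7.7.3 are always reportable. Section 2.3 describes the use as on label, so targeted reporting may be deliberate. All this is fair, and it limits the weight of the point. It does not reconcile 7.7.1 with 6.4, or explain why the fourth event of interest is missing from the list.

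**Stronger readings a reader might infer.**
- That unrelated non-serious events will be absent. The text says only that they need not be entered.
- That the rows for unrelated events will be almost empty. Unrelated serious events, and unrelated events of the three named types, still enter them.
- That entry depends on relation to a product given in one arm only. Relation to study procedures, which both arms undergo, also counts.
- That the comparison between arms is biased against the matrix. Unmasked judgement makes distortion possible, but equal capture gives no false difference, and nothing in the documents fixes the direction.

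**Conclusion.** The collection and analysis sections do not match. As written, the plan does not secure the data for the all-event tables and listing in 7.7.1, or for the fourth event of interest in 7.7.3. The affected events are the non-serious ones outside the three named types that are judged unrelated. Rates labelled as covering all events may be too low, and the comparison between arms may be distorted through an unmasked relatedness call.

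The size and direction cannot be known from the documents. The illustrative figures depend wholly on the assumed risks and capture rates. The conclusion takes 6.4 as defining what must be on the CRF; if the CRF in fact collects every event, the remaining defect is one of wording and is settled by saying so. The primary efficacy result is unaffected. The change is worth making because it determines what the safety tables can show.

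**What to change.** **Preferred.** In 6.4 and 6.3, require every adverse event from randomization to study exit to be entered on the CRF and graded for severity, seriousness and relatedness, in both arms. Keep the current 6.4 list solely as the list for prompt reporting. Add the fourth 7.7.3 event to it, so that the two lists agree.

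**Fallback.** If full entry is not wanted, label the 7.7.1 tables and listing as reportable adverse events, define that term by reference to 6.4, and drop the claim to all-event incidence. The fourth 7.7.3 event should still be added to those always entered on the CRF. This makes the tables accurate about their content, but other non-serious, unlisted events would still depend on the relatedness call.

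**Cost.** The preferred change means modest extra CRF entry and grading for 48 patients, over about 14 weeks each (12 weeks of treatment plus the 2-week confirmation visit), for events that sites already record under 6.1. The fallback costs a change of titles and one added event type.
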